# **Identifying risks of SARS-CoV-2 outbreaks in work settings and the implications for control measures**

### **(i) Study design**

This is a 5-year study comprising of a randomized controlled trial (RCT), a longitudinal quantitative study, a longitudinal qualitative study and a longitudinal workplace hygiene study in 3 selected non-healthcare work settings (i.e., non-office, mobile and office). The RCT will be implemented at the earliest stage of the project and completed in the first 2 years to generate short-term impact of research and inform policy. The 3 parallel longitudinal studies will be commenced in the 1.5th year and completed in the timeline of 4.5th year, and thus they would provide both the short-term and long-term impact of the research. The layout of overall study design and workflow chart is shown in **Figure 1**.

[figure not shown]
The choice of longitudinally repeated measurement using a mixed method of both quantitative and qualitative methods is made for the purpose of exploration of the possible new phenomenon of awareness and uptake of vaccination of virus tests over time among Hong Kong workers. Results from the longitudinally repeated workplace hygiene studies (e.g., airflow rate/direction, change volume of fresh air, etc.) would provide timely evidence on informing and enhancing the series of repeated quantitative surveys among workers over time.

### **(ii) Subjects to be included**

**Study subjects:** In the Part I randomized controlled trial (RCT), 294 eligible workers from 3 non-healthcare work settings will be recruited, and randomized into intervention group (147 subjects) and control group (147 subjects). To be eligible to the Part I RCT, all participants are required to be aged 18 or above, who can read Chinese and currently being employed in three non-healthcare work settings from non-office, mobile, and office work environment in Hong Kong. We attempt to follow-up all participants of the RCT for 9 months to observe the effectiveness of the intervention on improving the primary outcomes, i.e., attitude to vaccination and SARS-CoV-2 testing.

In Part II longitudinal quantitative study, we plan to recruit a total of 1,495 workers who are aged 18 or above and currently working in non-office, mobile, or office work setting in Hong Kong. All eligible study subjects in Part II longitudinal/ prospective cohort study will be recruited in the timeline of 1.5th -3.5th year of the project and followed up for 2 years to observe the changes of attitude to vaccination and virus testing as well as risk profiles of workers towards outbreaks over time.

Figure 1. Workflow chart of hazard identification of outbreaks and control measures in work settings

\* After considering a lost-to-follow-up rate of about 40%

In the Part III longitudinal qualitative study, we plan to recruit an overall 26 management staff and frontline workers (in a ratio of 1:2) with same inclusion/exclusion criteria as the Part I & II study, i.e., aged 18 or above and currently being employed in three non-healthcare work settings from non-office, mobile, and office work environment in Hong Kong.

All above planned number of participants to be enrolled in the baseline of the Part I, II and III study have already considered a potential loss-to-follow-up rate of about 40%.

**Settings:** The 3 work settings are categorized by types as below according to their job nature and working environment:

- (1) Non-office work: Workers normally carry out their jobs with a range of environment in an indoor or outdoor working space where close contact with the general public is frequent, and thus non-office work settings are considered at a higher risk of COVID-19 than the office work settings. Workers in non-office settings mainly include construction, accommodation and food service (e.g., hotel, restaurant), art/entertainment and recreation, professional bus drivers, outdoor instructor, real estate, wholesale and retail trades, etc.
- (2) Mobile work: Workers who frequently move within or in and out of Hong Kong for conducting business that involves closer and more frequent contact with the general public than the non-office workers, thus their risks to contracting COVID-19 are regarded to be the highest among 3 selected work settings. Workers in mobile work settings mainly include taxi drivers, food delivery workers, courier delivery workers, police officer, etc.
- (3) Office work: Workers normally carry out professional duties and administrative work in an indoor working space, such as an office or a room. Although the details of the job nature depend on the type of business to be involved, office work usually include using computers, communicating with others by telephone or fax, keeping records and files, etc. In general, office work offers relatively stable working environment where close contact with the general public is less frequent, and thus is considered having a low risk of contracting COVID-19 in the workplace. Workers in office work setting mainly include clerical workers, administrative workers, computer technicians, information and communication workers, etc.

**Sample size:** We estimated sample size for the Part I – Randomized controlled trial according to two independent proportions power analysis. As there is no relevant data of willingness to vaccination on our target subjects to guide the sample size calculation regarding an educational intervention against COVID-19, we employed a conservative assumption that the intervention will make a 20% change for worker's attitude to vaccination/virus test, sample size for both groups/arms will be 124, 130, 124, 109 and 79 for the proportion of willingness to vaccination/virus test of 30%, 40%, 50%, 60%, and 70%, respectively, with a 90% G-power. Therefore, a minimal 79 pairs subjects are required to achieve the primary objective (RCT) of this proposal project; if further assuming a loss-to-follow-up rate of about 40%, then an overall 222 participants with 111 subjects in the intervention group and 111 subjects in the control group are required. However, if given the most conservative sample size estimation with 40% loss-to-

follow-up rate, a total of 364 subjects with 182 subjects in each arm of RCT ( $130*1.4$ ) are required. Therefore, the overall sample size for RCT could reasonably range from 222 to 364 to satisfy the primary research objective of this proposal project. In the proposed RCT, we considered taking the mean of the “most-least conservative” sample sizes of 294 [ $(222+364)/2$ ] from G-power as a reasonable sample size with 147 subjects in each arm, and this sample size (i.e., 294) has already taken into consideration a potential loss-to-follow-up rate of about 40%.

We estimated sample size for the Part II – Longitudinal/prospective cohort study (quantitative survey) according to the formula for cohort studies. As there is no relevant publication for a reference, a conservative estimation is used to calculate the sample size for Part II study. For the estimation of the maximum sample size of longitudinally quantitative survey for the Part II study, the presumed population proportion is set as 0.5, which means that half of the workers have positive attitude to vaccination or willingness of SARS-Cov-2 virus testing in the selected work settings. It is estimated that a minimum of 1,068 workers is required for the longitudinal/prospective cohort study to accept an absolute sample error of 3.0% at 95% confidence level. Currently, there is not enough guideline for choosing an appropriate absolute error, and an absolute error of 5% is generally recommended in many studies. So, an absolute error of 3.0% employed in the project is more conservative than many other studies for sample size estimation. Although the required sample size is getting larger with the increase of population size, it will not change much when the population size is larger than 20,000. According to the latest statistics of the Census and Statistics Department of Hong Kong, the employed persons during 12/2020 - 2/2021 in Hong Kong are about 3.6 million, and therefore, it is appropriate to adopt this method of sample size calculation for a population-based cohort study in Hong Kong working settings. Assuming a potential loss-to-follow-up rate of about 40%, 1,495 workers are suggested to be recruited in the baseline survey for the Part II study.

While there is no established requirement for sample size estimation for the Part III and IV study which only involve qualitative approach and workplace hygiene measurement, it usually desires a reasonable sample size with representative sample. We plan to recruit 26 ( $18*1.4$ ) eligible subjects at the baseline from 3 defined work settings to participate in the Part III qualitative study and 6 representative workplaces for the Part IV study that are regarded as reasonable. We set the sample size according to number of participants/workplaces estimated to reach data saturation.

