### *(iii.1) Procedure of Part I study*

**Part I** is a 9-month **randomized controlled trial** to be conducted with single blinding and concealment during Year 1-2 (as shown in **Figure 1**).

**Study subjects of the RCT:** Two hundred ninety four workers from non-office, mobile and office work settings will be invited to participate in the RCT. The aim of the RCT is to test the hypothesis that a 9-month intervention program improves primarily the attitude towards vaccination and COVID-19 testing, with impact on the improving the actual uptake of COVID-19 testing and risk profile toward outbreaks at workplace.

**Procedures of the RCT:** All 294 participants will be randomized to intervention group and control group. Intervention group will receive theory-based educational intervention using the Theory of Planned Behaviours (TPB) PLUS general health information, while the control group will receive only general health information. As this RCT will investigate factors that can explain worker's intention to vaccination and virus testing, the theoretical framework using the theory for planned behavior (i.e., TPB) is a proper approach for improving workers' attitude toward SARS-CoV-2 and raise their intention to vaccination and virus testing. The intervention will be implemented at the baseline with measurements repeated at the 3rd month, 6th month and 9th month. The standardized mode of intervention includes face-to-face/online seminar (depends on the COVID-19 situation), message via mobile phone, promotion pamphlet, etc.

Primary outcomes of the RCT include attitude to vaccination and virus testing, and the secondary outcomes of the RCT are actual uptakes of virus antibody testing and changes of risk profile toward outbreaks in the workplace.

Key contents of intervention would include:

- TPB intervention: building positive attitudes towards COVID-19 related preventive behaviour (e.g., good compliance with infection control measures, encouraging uptake of testing and vaccination), subjective norms (tackling strategies for perceived social pressure from others or normative beliefs), and improving perceived behavioural control towards risks of outbreaks in workplace.
- Other necessary information: basic knowledge of SARS-CoV-2, chain of infection, health and social consequences of infection, general infection control measures, workplace engineering and administrative control measures.

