### ***(iii.5) SARS-CoV-2 antibody rapid test***

All participants of the RCT who do not finish COVID-19 vaccination will be invited to take the SARS-CoV-2 antibody rapid test four times points during the study to observe their attitudes toward antibody tests and their actual updates of the testing and compare the differences between the intervention and control group, i.e., at baseline, 3rd month, 6th month and 9th month of the RCT. We are also interested in inviting and welcoming those already with complete vaccination to participate in the SARS-CoV-2 antibody rapid test to understand their attitudes towards antibody testing and actual uptakes, and same primary outcomes between the intervention and control arms will be compared. The self-sampling test kit will detect the IgG/IgM antibody of SARS-CoV-2 from whole blood with above 90% sensitivity and specificity, which is recommended by US FDA.

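### Fully vaccinated workers are enrolled in the RCT, but the vaccination outcome is sized and analysed as if every participant could still change; analyse it by baseline vaccination status

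*Combined protocol and SAP*

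**What the plan says.** **Who is enrolled.** Section (ii) sets the RCT criteria: "all participants are required to be aged 18 or above, who can read Chinese and currently being employed in three non-healthcare work settings". Vaccination status is not among them. Section (iii.5) divides RCT participants by status. It begins "All participants of the RCT who do not finish COVID-19 vaccination will be invited" and goes on to speak of "inviting and welcoming those already with complete vaccination to participate in the SARS-CoV-2 antibody rapid test". The trial therefore expects both groups, and their shares are not given.

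**The outcome.** Section (iii.1) states: "Primary outcomes of the RCT include attitude to vaccination and virus testing". Measurements are taken at baseline and repeated at months 3, 6 and 9. No instrument, scale, cut-off or primary time point is given. The intervention content includes encouragement to be vaccinated, but vaccine uptake is not an RCT outcome.

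**The sizing.** The sample-size paragraph of section (ii) assumes that "the intervention will make a 20% change for worker's attitude to vaccination/virus test" and gives group sizes "for the proportion of willingness to vaccination/virus test of 30%, 40%, 50%, 60%, and 70%, respectively". This is a binary endpoint with a single shift for the whole sample.

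**The analysis.** Section (iv) allows linear models for a continuous outcome or Cox models for a binary one, with intention-to-treat to deal with loss to follow-up. It does not mention vaccination status.

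**The concern.** A worker who has completed vaccination before randomisation has already done what the intervention encourages. If the endpoint is willingness to be vaccinated, that worker will almost always count as willing in either arm and adds nothing to the contrast. The plan's 20 points would then have to come entirely from the remaining workers, although all 294 are counted towards the power.

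The second difficulty arises after randomisation. Someone persuaded and vaccinated between visits may later answer that the question no longer applies, or say no because it is done. If such answers are dropped or scored as unwilling, some of the intervention's successes leave the numerator. The plan has no rule for this.

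What is at stake is a vaccination result that is weak or hard to interpret even if the intervention works as assumed in workers who could still change.

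**Working it through.** **1. Reproduce the plan's figures.** Inputs from the sample-size paragraph are a 20-point difference, 90% power and starting proportions of 30 to 70%. Section (iv) gives the 0.05 level; two-sided is assumed because it reproduces the figures. The pooled two-proportion formula is

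n = [1.96·√(2p̄(1−p̄)) + 1.282·√(p₁(1−p₁)+p₂(1−p₂))]² / d²

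It gives 124, 130, 124, 109 and 82 per arm, against the plan's 124, 130, 124, 109 and 79. The arcsine formula gives 125, 130, 125, 108 and 79. The plan's numbers are thus those of a 20-percentage-point shift applied to every participant.

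**2. Let a share v be unable to change.** Assumptions, not in the documents: all fully vaccinated workers count as willing in both arms, and the others are at 40% vs 60%, the case for which the plan needs most subjects (130 per arm). Then

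- control p₁ = v + 0.4(1−v)
- intervention p₂ = v + 0.6(1−v)
- difference d = 0.2(1−v)

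**3. Power.** Power = Φ{[d − 1.96·√(2p̄(1−p̄)/n)] / √([p₁(1−p₁)+p₂(1−p₂)]/n)}.

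Example, v = 50% and n = 147: p₁ = 0.70, p₂ = 0.80, p̄ = 0.75. The numerator is 0.100 − 1.96 × 0.0505 = 0.0010 and the denominator is 0.0502, so the ratio is 0.02 and power is 51%.

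The table adds the analysis limited to workers not fully vaccinated at baseline, which is 40% vs 60% with n(1−v) per arm. The 88 per arm is 147 × 0.6 = 88.2, the plan's own 40% loss.

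| v | p₁ vs p₂ | d (points) | All, 147/arm | Not fully vaccinated, from 147/arm | All, 88/arm | Not fully vaccinated, from 88/arm |
|---|---|---|---|---|---|---|
| 0 | 40 vs 60% | 20 | 93% | 93% | 76% | 76% |
| 25% | 55 vs 70% | 15 | 76% | 85% | 54% | 64% |
| 50% | 70 vs 80% | 10 | 51% | 68% | 33% | 47% |
| 75% | 85 vs 90% | 5 | 25% | 40% | 17% | 26% |

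The smaller group gives more power at every v above zero. For 90% power in the pooled comparison at v = 50%, 392 per arm would be needed instead of 130.

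**4. Coding of workers vaccinated during follow-up.** Illustration: of 100 per arm, 40 and 60 are truly willing.

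- Half of the willing are vaccinated in each arm (20 and 30). Dropped: 20/80 = 25% vs 30/70 = 43%. Scored unwilling: 20% vs 30%.
- Unequal uptake, 20 of 40 and 40 of 60. Dropped: 20/80 = 25% vs 20/60 = 33%. Scored unwilling: 20% vs 20%.
- Counted as willing, whatever the uptake: 40% vs 60%.

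The observed contrast can therefore lie anywhere from close to 20 points down to zero, depending on the coding rule and on uptake by arm. The documents supply neither.

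**The case against.** The strongest reply is that the named outcome is attitude, not willingness. Section (iv) refers to scores and allows linear models, and no text confines vaccination to a first course. An attitude score, or an item about further doses, can still move in a vaccinated worker. This stands: the ceiling is firm only for a binary willingness item about initial vaccination. But that binary form is the only one the plan sizes. If a score is intended, the sample size does not match the endpoint, and the text needs correcting anyway.

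Second, section (iv) names Cox models for binary outcomes. If the event were first becoming willing, a worker willing at month 3 and vaccinated at month 4 would already have had the event, and workers willing at entry would normally not be at risk. That would remove most of the coding problem. The event is not defined, however, and under that reading fewer than 294 workers contribute, which the sizing does not allow for.

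Third, an effect averaged over all employed workers is a legitimate target, and dilution is not bias. Agreed. The power must then be computed for that average, and it was not.

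Fourth, section (iii.5) says "same primary outcomes between the intervention and control arms will be compared" in connection with vaccinated workers. The sentence concerns the antibody test; it sets out no analysis of the vaccination outcome by status.

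A reader might go further and infer that a working intervention would show a null at month 9, or that the result is biased against it. The documents do not support that. No text makes month 9 primary, none scores vaccinated people as unwilling, and the 20% vs 20% result needs both that rule and unequal uptake. With equal uptake and exclusion the difference is still 18 points (43% − 25%).

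**Conclusion.** The concern holds conditionally. If the vaccination outcome is analysed in the willing/unwilling form used for sizing, pooling all participants regardless of baseline vaccination shrinks the expected difference to about 20(1−v) points. Power falls from 93% at v = 0 to 76, 51 and 25% at v = 25, 50 and 75% with 147 per arm, and from 76% to 54, 33 and 17% with 88 per arm. These figures rest on three assumptions: 40% vs 60% in workers not fully vaccinated, every vaccinated worker counted willing, and a share v that the documents do not give.

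Miscoding of workers vaccinated during follow-up is a further risk of unknown size; it strengthens the case for a written rule but does not establish bias. The primary outcome on attitude to testing is not affected.

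**What to change.** 1. **Sections (iii.1) and (iii.5):** record vaccination status before randomisation and at each visit. The antibody-test invitation already depends on status, so this adds one short item per visit.
2. **Section (iv):** analyse the vaccination outcome by baseline vaccination status. A stratified or adjusted analysis can keep all 294, with the estimate in workers not fully vaccinated at baseline pre-specified as primary or key. This group is defined before randomisation, so the comparison within it remains randomised. Restricting the whole analysis is not the only sound choice: if all vaccinated workers count as willing, a stratified comparison uses the same information. Keep all participants for the testing outcome.
3. **Sections (iii.1) and (iv):** state that a participant vaccinated after randomisation counts as willing at every later visit, and fix this rule before any comparison by arm. If a score or an item on further doses is intended, define it and size the trial on it.
4. **Sample-size paragraph of section (ii):** state that the 20-point change and the power refer to workers not fully vaccinated at baseline, and restate the power for the expected share.

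The cost is protocol and analysis wording plus the status item. The estimate in the not fully vaccinated will use fewer than 294 people, and its conclusion will apply only to them. The change recovers part of the power (for example 51% to 68% at v = 50% with 147 per arm, or 33% to 47% with 88) but does not bring it back to 90%; doing so would need more participants.

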### **(iv) Data processing & analysis**

For quantitative results, descriptive analysis and Chi-square will be used for baseline data to analyse the difference in exposure and prevention, willingness to vaccination/testing and actual uptake of tests between comparison groups (e.g., work settings). Paired t-test and covariance analysis will be performed to compare the longitudinal changes of scores of each exposure prevention behaviour factors, attitude and willingness to vaccination and virus testing over time. Structural equation modelling and multivariate regression logistic modelling will be used to analyze the structural relationship between measured variables and latent constructs, as well as examine the association of exposure profile with willingness to vaccination/testing or uptake testing. Effectiveness of intervention will be examined by multivariable linear (for continuous nature of outcome) or Cox proportional hazard models (for binary outcome). Loss-to-follow-up will be reported and intention-to-treat analysis will be used for addressing the loss-to-follow-

up issue of the RCT. All statistical analyses for longitudinal quantitative and RCT data will be conducted by SPSS Version 26 and/or SAS 9.4 (SAS Institute Inc., North Carolina). P-value of less than 0.05 is considered statistically significant.

For qualitative analysis, the tape-recorded individual interviews will be transcribed verbatim and thematically analysed using Grounded Theory approach. Data will be horizontally compared between participants, and longitudinally analysed, tracking and explaining attitudinal and behavioral changes of individuals across time. The qualitative data will be delineated to a typology of reasons for (1) accepting, delaying or refusal of COVID-19 vaccine, and (2) factors contributing to uptake of COVID-19 testing in the workplace, generated through thematic analysis.

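### The trial's attitude outcomes are sized as proportions at 90% power, which the completers expected after 40% loss do not give in four of five scenarios, and the plan does not say whether score or proportion is primary

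*Combined protocol and SAP*

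**What the plan says.** Section (iii.1), Procedure of Part I study, defines the outcomes: "Primary outcomes of the RCT include attitude to vaccination and virus testing". It gives no scale and no cut-off.

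Section (ii), Sample size, treats them as yes/no. The trial is sized "according to two independent proportions power analysis", assuming that "the intervention will make a 20% change for worker's attitude to vaccination/virus test". The requirements per arm are "124, 130, 124, 109 and 79 for the proportion of willingness to vaccination/virus test of 30%, 40%, 50%, 60%, and 70" per cent, "with a 90% G-power". The smallest and largest are multiplied by 1.4 for 40% loss, giving totals of 222 and 364. Their mean is taken as 294, or 147 per arm.

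Section (iv), Data processing & analysis, plans paired t-tests and covariance analysis for changes in "scores of each exposure prevention behaviour factors, attitude and willingness to vaccination and virus testing over time". On the effect of the intervention it says: "Effectiveness of intervention will be examined by multivariable linear (for continuous nature of outcome) or Cox proportional hazard models (for binary outcome"). It does not say which branch applies to the attitude outcomes.

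**The concern.** Two things do not fit together.

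- **Power.** The stated 90% belongs to completer numbers of 79 to 130 per arm. The number recruited and the expected loss leave fewer completers than four of the five scenarios need.
- **Scale.** The sample size uses a proportion, the analysis section mentions scores, and the effectiveness sentence covers both. A mean difference and a difference in the proportion willing are different target quantities. If the choice is made after the data are seen, each attitude outcome has two routes to significance.

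At stake are a trial with roughly three-in-four power in its middle scenarios, and a primary result whose scale was not fixed in advance. The suitability of a Cox model, the number of primary outcomes and the choice of follow-up time are separate matters.

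**Working it through.** **Inputs.** From section (ii): base proportions 30 to 70%, a 20% change, 90% power, 147 per arm, 40% loss. From section (iv): "P-value of less than 0.05 is considered statistically significant". The change is read as +20 percentage points and the test as two-sided, because these readings reproduce the plan's figures.

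**1. The plan's sample sizes.** With p2 = p1 + 0.20 and m = (p1 + p2)/2,

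n = {1.96 √[2m(1−m)] + 1.2816 √[p1(1−p1) + p2(1−p2)]}² / 0.20².

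This gives 124, 130, 124, 109 and 82. The first four match. The fifth, stated as 79, matches the unpooled-variance and arcsine versions. One-sided sizes (101, 106, 101, 89, 67) do not match.

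**2. Recruitment.** 79 x 1.4 = 110.6, so 111 per arm (222). 130 x 1.4 = 182 per arm (364). (222 + 364)/2 = 293, stated as 294.

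**3. Completers.** 147 x 0.6 = 88.2, so 88 per arm. The 1.4 factor treats 147 as if it left 147/1.4 = 105. To keep 130 completers after 40% loss, 130/0.6 = 217 per arm are needed.

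**4. Power for the proportion.** Power = Φ{(0.20 − 1.96 √[2m(1−m)/n]) / √[(p1(1−p1) + p2(1−p2))/n]}.

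| Base willing | n = 105 | n = 88 |
|---|---|---|
| 30% | 85% | 78% |
| 40% | 83% | 76% |
| 50% | 85% | 78% |
| 60% | 89% | 83% |
| 70% | 96% | 92% |

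The n = 105 column shows the cost of averaging the extremes alone. The n = 88 column adds the cost of inflating by 1.4.

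**5. Power for a score, conditional on an assumption.** The documents give no score range, SD or mean difference. Assume a normal score, shifted as a whole by the intervention and cut at the yes/no threshold. Then d = z(p2) − z(p1), and power = Φ(d √(88/2) − 1.96).

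| Base willing | d | Score power |
|---|---|---|
| 30% | 0.52 | 94% |
| 40% | 0.51 | 92% |
| 50% | 0.52 | 94% |
| 60% | 0.59 | 97% |
| 70% | 0.76 | 99.9% |

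For one five-category item, with equal control categories, the 40% scenario gives 89%. Power of 90% needs d = (1.96 + 1.2816) √(2/88) = 0.49. At d = 0.4, 0.3 and 0.2 it is 76%, 51% and 26%.

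**6. When the assumption fails.** Take a five-point item with control categories 10/20/30/25/15%, so 40% are willing (top two categories). Mean 3.15, variance 1.4275. Each intervention pattern below has 60% willing, so power for the proportion stays at 76%.

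| Intervention arm | Mean difference | SE | Score power |
|---|---|---|---|
| 10/20/10/45/15% | 0.20 | 0.183 | 19% |
| 10/10/20/45/15% | 0.30 | 0.178 | 39% |
| 5/15/20/40/20% | 0.40 | 0.174 | 63% |

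First row: Φ(0.20/0.183 − 1.96) = Φ(−0.87) = 19%.

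**7. Either scale counted as success.** Simulating no effect with 88 per arm, a normal score and cut-offs at 30, 50 and 70% willing, each test alone rejects about 5% of the time. At least one rejects about 8% of the time.

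**The case against.** Four points can be made for the plan, and each limits what may be concluded.

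- **Score and power.** A reader might infer that analysing the score would simply restore 90% power. The documents do not support that. They give no SD or mean difference, and steps 5 and 6 show score power from 19% to 99.9% depending on how the intervention acts. An educational programme that converts undecided workers is as plausible as one that shifts everybody. This objection stands in full.
- **Two tests.** A reader might also infer that the plan schedules two tests per outcome. It does not. The effectiveness sentence matches the model to the type of outcome, and uptake of testing, a secondary outcome, is naturally binary. The 8% describes what the open wording would permit, not a planned procedure. The ambiguity remains, because the attitude outcomes appear once as proportions and once as scores.
- **Scored RCT outcomes.** The mention of scores stands in a general paragraph, and the questionnaire is described under Part II. That the RCT scores attitude is therefore an inference. It is a reasonable one, since the same paragraph contains the sentence on effectiveness and says that it covers the RCT data.
- **Cause and preference.** The shortfall is not caused by using a proportion. It comes from averaging and from the 1.4 factor, and at 70% willing there is none. The proportion willing is also a legitimate and readable target. Both are true, so the power of the proportion must be corrected openly and the proportion still reported.

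**Conclusion.** The concern holds in this form. The plan implies 90% power for the proportion willing, but at 88 completers per arm it has 76 to 92% and falls short in four of five scenarios. This rests on the plan's own 20-point effect and 40% loss, a two-sided 0.05 test, and no information recovered from workers lost. The plan names an intention-to-treat analysis but no method for missing data.

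The primary scale is open. Fixing it removes a possible rise in type I error from 5% to about 8% per outcome.

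Making the score primary needs no extra participants and may also gain power. That gain is conditional: about 90% if the effect is a whole-distribution shift of about 0.5 SD, and less otherwise, possibly below the proportion. The change should be made, but the score's power must not be presented as established.

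**What to change.** - **Sections (iii.1) and (iv):** name the attitude score, compared between arms by the linear model already listed, as the one primary scale for each attitude outcome. Define its items and range. Keep the proportion willing as a supportive analysis, with its cut-off fixed before any comparison of the arms.
- **Section (ii), Sample size:** restate power for the proportion at 88 completers per arm as 76 to 92% across the five scenarios. State power for the score as conditional: about 90% for a shift of about 0.5 SD, 76% for 0.4 SD and 51% for 0.3 SD.

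**Cost.** Changes to the text and a definition of the score, with no added recruitment. Score points are less intuitive than a percentage willing, and the score can have less power if the intervention mainly carries undecided workers over the cut-off. Both results should therefore be reported. If the sponsor prefers to keep the proportion primary at 90% power in the hardest scenario, step 3 gives 217 per arm.

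### The RCT's 20-point planning effect is called conservative without support, and at the plan's own 40% loss the trial falls short of 90% power for it unless about 70% of workers are already willing

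*Combined protocol and SAP*

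**What the plan says.** The Sample size paragraph of section (ii) sizes the RCT "according to two independent proportions power analysis". It states that "there is no relevant data of willingness to vaccination on our target subjects to guide the sample size calculation" and then, "we employed a conservative assumption that the intervention will make a 20% change". It gives 124, 130, 124, 109 and 79 per arm for willingness of 30%, 40%, 50%, 60% and 70%, "with a 90% G-power". Only the willingness proportion is varied; the effect stays fixed.

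The smallest and largest sizes are multiplied by 1.4 for a 40% loss, giving totals of 222 and 364. Their mean is taken as 294, or 147 per arm. The plan names no minimum important difference, gives no scenario with a smaller effect, and does not say what difference the retained sample can detect.

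On significance, section (iv) says only "P-value of less than 0.05 is considered statistically significant". It does not commit to reporting an effect estimate with a confidence interval, and has no rule for interpreting a non-significant result.

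**The concern.** In a sample-size calculation, a cautious effect assumption is a small one, because it asks for more participants. The document uses the word that way elsewhere: it calls the 130-per-arm case the most conservative, and in Part II it calls a 3% error more conservative than the usual 5%. Applied to a 20-point effect chosen without data, the word suggests a safety margin that the paragraph does not demonstrate.

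The second issue is what the final 294 delivers. A reader would take the paragraph to mean 90% power for 20 points after the stated loss. If that is not so, the plan overstates the trial's sensitivity, and a non-significant result could be given more weight than it can bear. Section (i) intends the RCT to inform policy, so this matters.

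**Working it through.** **Inputs.** From section (ii): control proportions 30–70%, a 20% change, 90% power, 147 per arm, loss about 40%. From section (iv): significance level 0.05. The plan does not state whether the test is two-sided; two-sided is assumed because it reproduces the stated sizes (one-sided gives 101, 106, 101, 89, 67).

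**1. Reproduce the plan's sizes.** With p₂ = p₁ + d and p̄ the mean of the two proportions:

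n = [1.960·√(2p̄(1−p̄)) + 1.282·√(p₁(1−p₁) + p₂(1−p₂))]² / d²

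For d = 0.20 this gives 124.0, 129.3, 124.0, 108.2 and 82.0, against the stated 124, 130, 124, 109 and 79. The unpooled and arcsine formulas both give 79 for the last row, so that gap is a choice of formula. A relative 20% increase would need 188 to 1,289 per arm. The plan's 20% is therefore 20 absolute points.

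**2. Direction of the assumption.** At 40% willing and 90% power, the formula requires 130 per arm for 20 points, 231 for 15 and about 519 for 10. Raising the assumed effect lowers the sample.

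**3. Retained number.** 79 × 1.4 = 110.6, so 111 per arm and 222 in total. 130 × 1.4 = 182 per arm and 364 in total. (222 + 364)/2 = 293, which the plan takes as 294. A 40% loss leaves 147 × 0.6 = 88.2, about 88 per arm. That is below four of the five stated sizes.

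**4. Power and detectable difference at 88 per arm.**

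Power = Φ{[d√n − 1.960·√(2p̄(1−p̄))] / √(p₁(1−p₁) + p₂(1−p₂))}

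Example at 40% willing, d = 0.20: (0.20 × 9.381 − 1.960 × 0.7071)/0.6928 = 0.708, and Φ(0.708) = 0.76.

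| Willing in control arm | Power for 20 points | Detectable, 90% power | Detectable, 80% power |
|---|---|---|---|
| 30% | 78% | 23.8 points | 20.6 points |
| 40% | 76% | 24.1 | 21.0 |
| 50% | 78% | 23.5 | 20.5 |
| 60% | 83% | 21.9 | 19.3 |
| 70% | 92% | 19.4 | 17.2 |

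**5. Where the shortfall comes from.** If 130 per arm were retained, the 90%-power detectable difference would be 16.5 to 20 points, as planned. Retaining 130 after a 40% loss needs 130/0.6 = 217 per arm, not 182; for 79 it needs 132, not 111. The excess over 20 points thus arises from averaging the extremes and from multiplying by 1.4 instead of dividing by 0.6.

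**6. Smaller effects.** The plan names no useful difference, so 10 points is an assumption for illustration. Power for 10 points is 26–33% at 88 per arm and 41–51% at 147. The 95% interval half-width with both arms at the same proportion is 1.96·√(2p(1−p)/n). Across 30–70% willing it is 13.5 to 14.8 points at 88 per arm and 10.5 to 11.4 at 147. An estimate of zero would not exclude a 10-point gain in either case.

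**The case against.** - **The label cannot be shown to be false.** An assumed effect is conservative only relative to the effect expected, and the plan gives none. A reader might infer that 20 points is demonstrably optimistic, or note that at 70% willing it means converting 0.20/0.30 = 67% of unwilling workers. But at 30% willing the same change is 0.20/0.70 = 29%, and the final 294 is not the 70% row's size. This objection stands: the label is unsupported, not disproved.
- **Nothing says 10 or 15 points would be useful.** A reader might infer that the trial detects only large changes and misses useful ones. The documents do not support that. What counts as large or useful is not defined, and with no loss the 80%-power detectable difference is 14–16 points. This also stands.
- **The planned analysis may be more sensitive.** Section (iii.1) repeats measurements at months 3, 6 and 9, and section (iv) allows covariance analysis of scores and linear models. That is possible, but no standard deviation or correlation is given to quantify any gain, and the plan sizes the trial on two proportions.
- **Intention-to-treat is planned to address loss.** Section (iv) names no method for missing outcomes, so it gives no basis for treating the full 147 per arm as observed.
- **The harm is speculative.** No passage says that a non-significant result will be read as no effect. That is correct; the point is that no passage guards against it either.

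**Conclusion.** The point holds in a limited form. The 20% is an absolute 20-point change, and calling it conservative has no support in the plan and runs against the document's own use of the word. Separately, the stated 90% power for 20 points is not met at the plan's own 40% loss unless willingness is near 70%. Power is 76–78% at 30–50% willing, 83% at 60% and 92% at 70%.

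It would be wrong to attribute that shortfall to the label. It follows from the averaging and the 1.4 multiplier, and should be counted once, together with any comment on those steps.

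The figures assume a two-sided 0.05 test, 88 retained per arm, and an unadjusted binary comparison at one time point. They do not carry over directly to a continuous or repeated-measures analysis.

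**What to change.** In section (ii), Sample size: delete the word conservative from the effect assumption and say that the 20% is an absolute 20-point planning value. In place of the implied 90% power for 20 points, state the differences detectable with 80% and 90% power at the number expected to be retained. At 88 per arm these are 17–21 and 19–24 points.

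In section (iv): report each primary comparison as an effect estimate with a 95% confidence interval on the scale of the outcome analysed (a difference in proportions if binary, a mean difference if continuous). Say that a non-significant result will be interpreted from that interval, not from the p-value alone.

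The cost is wording in two sections and a less favourable statement of power. No extra participants, visits or data are needed. The change makes the plan's description accurate; it does not raise the power.
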